controlled design with 374 cancer patients, we will: 1) Compare standard varenicline treatment (12-weeks active + 12-weeks placebo) to extended varenicline treatment (24-weeks active) for increasing week 24 and week 52 biochemically-confirmed 7-day point prevalence abstinence; 2) Assess the effects of extended varenicline therapy on QOL, including varenicline side effects; and 3) Assess changes in affect and cognitive impairment as mediators of extended varenicline therapy's effect on quit rates. We will also explore potential moderators of the effect of extended varenicline treatment on quit rates (e.g., tumor site and stage, time since diagnosis, treatment history, level of nicotine dependence). This study is significant by addressing a population with high smoking rates, which has been under-studied in the area of nicotine dependence treatment, and is at risk for unique adverse tobacco-related health effects. This study is innovative by evaluating the efficacy of extended vs. standard duration varenicline treatment, which may more effectively address unique barriers to cessation in this population. This will also be the first study to use varenicline blood levels as a measure of adherence. There is widespread agreement that evidence-based treatment programs for nicotine dependence among cancer patients are needed. This study may help guide efforts to implement such programs and help determine the benefits of extended treatment duration for nicotine dependence more broadly.

OBJECTIVES

1. Overall Objectives

Aim 1: Compare standard varenicline therapy (12-weeks active then 12-weeks placebo) to extended varenicline therapy (24-weeks active) for treating nicotine dependence among cancer patients.

Hypothesis: Extended varenicline therapy will increase 24- and 52-week biochemically-confirmed 7-day point prevalence abstinence, vs. standard varenicline treatment.

Aim 2: Assess effects of extended varenicline therapy on quality of life (QOL) and varenicline side effects. **Hypothesis:** QOL will be rated higher in the extended therapy group vs. the standard therapy group, and there will be no significant differences between groups in terms of severe side effects.

Aim 3: Assess changes in affect and cognitive impairment as mediators of extended varenicline therapy's effect on quit rates. **Hypothesis:** Improved affect and reduced cognitive impairment will mediate the effect of extended therapy on quit rates.

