Aim 1: The primary analysis is a comparison in Week 24 and Week 52 point prevalence quit rates between standard and extended therapy. For the week 24 comparison, we based our sample size on the expectation that the quit rate in the standard arm would be equal to the Week 24 quit rates reported in past clinical trials of varenicline for participants who received 12 weeks of treatment (i.e., 33%; Gonzales et al., 2006). We also expect to see at least the same effect on week 24 quit rates here as we saw in our past extended treatment trial (i.e., an OR of 1.81 or a difference of ~14%; [name] et al., 2010b). Thus, we have 80% power (alpha .05) with a sample of 374 if the difference between treatment arms in Week 24 quit rates is 14% (i.e., Week 24 quit rates for extended therapy is 47%). For the Week 52 comparison, we can expect a Week 52 quit rate for the extended arm of 56% (Tonstad et al., 2006), vs. 28% for standard treatment (Gonzales et al., 2006), for which we have 99% power (alpha = .05) with n = 374; we are powered to detect a difference at Week 52 of 14% if the present study yields a smaller effect than expected based on past studies.

Aim 2: The primary analysis is a comparison in Week 24 and Week 52 differences in QOL and severe side effects. For QOL, we have 80% power to detect a mean difference of 0.87 in physical QOL and a mean difference of 1.2 in mental QOL at any time-point, effects seen previously ([name] et al., 2010a). For side effects, the analyses will involve a test of non-inferiority since we cannot use standard statistical tests and conclude that a non-significant comparison means that the treatments are equal (i.e., “the absence of evidence is not evidence of absence”). In our past bupropion study ([name] et al., 2010a), 95% of placebo and 88% of bupropion participants reported no severe side effects. Assuming a similar difference, we have 90% power to detect equivalence with a floor of 80%, or an extended group that is 15% < the standard group.

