Aim 1: Compare standard varenicline treatment (12-weeks active then 12-weeks placebo) to extended varenicline treatment (24-weeks active) for treating nicotine dependence among cancer patients. The hypothesized effect of treatment arm (i.e., the difference in quit rates between subjects receiving standard or extended treatment) will be tested by a treatment arm term in a binomial family with logit link (logistic regression) model that possibly includes terms for covariates. Outcomes of the logistic regression analyses will be characterized by odds ratios (e.g., odds of quitting smoking) and 95% confidence intervals. Although quit-rates at the end of 24 and 52 weeks will represent our primary outcome variables, similar logistic regression analyses will be performed for other assessments of quit rates (e.g., quit rates at Weeks 12 and 26). This model will be used for measures of prolonged and continuous abstinence as well. In addition, as many participants will fail to become completely abstinent, the negative binomial family log link for count data will be used to examine the main effects of treatment arm on changes in smoking rate. Time to (recurrent) event models will be fitted using Cox regression, stratified by event sequence, as in [name] et al. (2010).

Aim 2: Assess effects of extended varenicline therapy on QOL and varenicline side effects. Repeated-measures MANOVA will examine differences across treatment arms in mental and physical QOL over the trial. Covariates will be included, such as medical treatment history. We will compare treatment arms in terms of the frequency of severe side effects (individual and total). Logistic regression will test against the lower boundary on percent reporting only mild-moderate (i.e., < severe) side effects. The hypothesis test for equivalence is whether the OR is out of the prescribed range for the difference between the treatment arms.

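### The Aim 2 side-effect test is worded in the reverse direction to the non-inferiority test that the Power section calls for, and its decision rule is not stated

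*Combined protocol and SAP*

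**What the plan says.** Three places in the combined protocol and SAP bear on this.

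- **Statistical Analysis, Power, Aim 2.** For side effects "the analyses will involve a test of non-inferiority since we cannot use standard statistical tests" and then "conclude that a non-significant comparison means that the treatments are equal". The planning rates come from an earlier bupropion trial: "95% of placebo and 88% of bupropion participants reported no severe side effects". Assuming a similar gap, the plan states that "we have 90% power to detect equivalence with a floor of 80%, or an extended group that is 15% < the standard group". Severe side effects are listed there as part of the Aim 2 primary analysis.
- **Statistical Analysis, Data Analysis, Aim 2.** Logistic regression is to test against a lower limit on the percentage of patients with nothing worse than mild or moderate side effects. The next sentence reads: "The hypothesis test for equivalence is whether the OR is out of the prescribed range for the difference between the treatment arms". No odds-ratio limits, hypotheses, confidence-limit rule or alpha follow.
- **Objectives, Aim 2.** The hypothesis is that "there will be no significant differences between groups in terms of severe side effects".

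**The concern.** In a non-inferiority test the null hypothesis is that the extended arm is worse by the margin or more, and the data must reject it. The Data Analysis sentence asks whether the odds ratio is outside the range. Read literally, this makes being inside the range the default, and equivalence is what remains when no departure is shown. That is the error the Power section warns against, moved from no difference to the margin. The Objectives wording has the same form.

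At stake is the Aim 2 statement that doubling treatment duration brings no unacceptable excess of severe side effects. An analyst following the Data Analysis sentence and one following the Power section could report opposite conclusions from the same data.

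**Working it through.** **Inputs.** N = 374 (Study Procedures). The allocation ratio is not stated; 1:1 is assumed, giving 187 per arm. The rates free of severe side effects are 95% standard and 88% extended, and the floor is 80%, i.e. 15 points (Power, Aim 2). Alpha is not stated for Aim 2; one-sided 0.05 and 0.025 are both used.

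**Step 1: the plan's 90% power.** Take a one-sample test of 88% against the 80% floor at one-sided 0.05.
- Null SE = √(0.80×0.20/187) = 0.02925. Alternative SE = √(0.88×0.12/187) = 0.02376.
- Power = Φ[(0.08 − 1.645×0.02925)/0.02376] = Φ(1.34) = 91%. At one-sided 0.025 it is 83%.

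Now take the two-sample risk difference against −15 points.
- SE = √(0.95×0.05/187 + 0.88×0.12/187) = 0.02861. The distance from the margin is 0.15 − 0.07 = 0.08.
- Power = Φ(0.08/0.02861 − 1.645) = Φ(1.15) = 87.5%. At one-sided 0.025 it is 79.8%.

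So the 90% is reproduced to within about a point by a test that must reject inferiority. A rule that declares equivalence unless harm beyond the margin is significant would succeed in about 100% of trials at 95% vs 88%, which nobody would report as 90%.

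**Step 2: both directions at the limit.** Set the true rates at 95% and 80%. On the risk-difference scale, z = (p_E − p_S + 0.15)/SE, with p_E and p_S the observed proportions free of severe side effects in the extended and standard arms. On the odds-ratio scale the margin is (0.80/0.20)/(0.95/0.05) = 0.21, and z = (log OR − log 0.21)/SE with a 0.5 continuity correction.
- Literal rule: declare equivalence unless z < −1.645 (or −1.96).
- Correct rule: declare non-inferiority only if z > 1.645 (or 1.96).

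At the limit z is roughly standard normal, so the literal rule should declare about 1 − α of the time and the correct rule about α. Exact enumeration of the two binomials, 187 per arm:

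| Rule | Scale | α = 0.05 | α = 0.025 |
|---|---|---|---|
| Literal | Risk difference | 95.2% | 97.8% |
| Literal | Odds ratio | 97.0% | 98.9% |
| Correct | Risk difference | 5.6% | 2.9% |
| Correct | Odds ratio | 6.3% | 3.4% |

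With 131 per arm (the roughly 70% follow-up expected under Accrual) the ranges are 95-99.5% and 3-6%.

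**Step 3: what the correct rule delivers at the planned rates.** Exact success at 95% vs 88%, 187 per arm:
- risk difference: 86.5% (one-sided 0.05) or 78.8% (0.025);
- odds ratio with the 0.21 margin: 47.3% or 36.1%.

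The odds-ratio margin also moves with the control rate. Expressed as odds of a severe side effect, 15 points is an odds ratio of 4.75 at 95% vs 80%, but (0.90/0.10)/(0.75/0.25) = 3.0 at 90% vs 75%.

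**The case against.** A reader might infer that the plan will conclude equivalence whenever harm is not shown, and so has no control over a false safety claim. The documents do not support that.

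- No section says so, and the Power section rejects that reasoning outright.
- The sentence just before the disputed one tests against a lower limit, as a non-inferiority test does.
- The disputed sentence assigns no null and no conclusion. It could even be read as naming the null to be rejected.
- The stated power fits only a correctly directed test.
- The Objectives sentence gives an expected result, not a decision rule.
- For individual effects the plan says only "We will compare treatment arms in terms of the frequency of severe side effects (individual and total"); it announces no conclusion of no difference.

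All of this stands, and it limits the finding to wording and an unstated rule. It does not dispose of it. The test against the lower limit does not say which side of the limit is the null, and nothing elsewhere supplies the hypotheses, the confidence limit or the alpha. The disputed sentence is the closest the plan comes to a decision rule, and its plain reading runs the wrong way.

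**Conclusion.** The point holds as an inconsistency with a possible large consequence. The Data Analysis and Objectives wording contradicts the non-inferiority rationale in the Power section, and the decision rule is undefined. The contrast of 95-99% with 3-6% is conditional: it describes what literal application would do, not what the sponsor is shown to intend. It rests on 1:1 allocation, a 95% control rate, a true extended-arm rate exactly at the floor, and one-sided alpha of 0.05 or 0.025. The contrast hardly depends on scale or on sample size between 131 and 187 per arm. Because this is part of the Aim 2 primary analysis, the rule should be settled before unblinding.

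**What to change.** Replace the disputed sentence under Data Analysis, Aim 2, with:

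*H0: the proportion free of severe side effects in the extended arm is lower than in the standard arm by 15 percentage points or more. Non-inferiority is concluded only if the lower confidence limit for the difference (extended minus standard), at a stated one-sided alpha, lies above −15 points; otherwise it is reported as not established.*

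Fill in the alpha and reconcile it with the general statement at the head of the Power section that comparisons are two-sided. Keep the margin in percentage points, as the Power section has it, for example through a risk difference derived from the logistic model. Reword the Aim 2 hypothesis under Objectives to non-inferior within the margin.

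This needs no new data or patients. The cost is a harder claim: at the planned rates, success falls from near certainty under the literal rule to about 87% or 79% (one-sided 0.05 or 0.025) with 187 per arm, and to about 75% or 65% with 131. Moving the margin to the odds-ratio scale would cost far more, with success of about 47% or 36% at 187 per arm, so the scale must be named.

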At PENN, a previous extended nicotine patch trial recruited a sample comprised of 45% women and 16% racial/ethnic minorities ([name] et al., 2010b); a separate PENN smoking cessation trial that used targeted efforts to recruit minority smokers had a sample comprised of 55% women and 52% racial/ethnic minorities ([name] et al., 2011). Further, 29% of the sample of cancer patients in [name] bupropion trial was African American and 48% were female ([name] et al., 2010a). At NU, a smoking cessation trial with fluoxetine recruited a sample comprised of 54% women and 38% ethnic/racial minorities (Spring et al., 2007). Lastly, 53% of cancer patients at PENN are women and 24% are from ethnic/racial minority groups and 54% of cancer patients at NU are women and 48% are from ethnic/racial minority groups.

2. Accrual

At PENN, the trial will be primarily implemented at the Abramson Cancer Center (ACC). [name], ACC Deputy Director, will ensure study integration within oncology clinics. ACC data indicate that the clinics to be used to recruit for this study saw ~3200 new patients in 2009. Preliminary data ascertained as part of an ongoing smoking cessation project for relatives of cancer patients (R01 CA126969) showed that, among 517 eligible cancer patients screened, 150 were currently smoking (29%) and 78 (52%) agreed to enroll in a smoking cessation program. Thus, based on ~3200 patients available for screening/year, we expect that ~925 will be smokers and ~480 will be interested in a smoking cessation program. Given the trial requirements and inclusion/exclusion criteria, we estimate that we can enroll ~10% of these patients for this trial (Martinez et al., 2009) or ~48 patients/year at PENN (total sample at PENN = 187 over 4 years).

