Smoking status is assessed using the timeline follow-back method (Brown et al., 1998) as done previously (Lerman et al., 2004; [name] et al., 2010b) and by using breath CO to verify self-report. Participants are considered abstinent if they self-report abstinence (not even a puff of a cigarette) for >7 days prior to the Week 24 and 52 assessment and have a breath CO of <10ppm at the time-point (SRNT, 2002; Hughes et al., 2003). As per convention, participants are assumed to be smoking if they self-report to be smoking at the time-point, cannot be reached to provide data at the time-point, fail to provide a breath sample at the time-point, or provide a breath sample at the time-point that is >10ppm (SRNT, 2002).

Cessation/Smoking Rate: Daily smoking (presence and rate) will be assessed at each visit after Intake Session with the well validated timeline followback method (TLFB). These data can be used to assess

the timing and rates of lapses (smoking episodes not lasting 7 days), recovery events (return to abstinence), and relapse events, as well as to monitor changes in smoking rates (i.e., # cigarettes/day). These data will also be used to compute and assess secondary measures of smoking cessation (e.g., continuous and prolonged abstinence).

Carbon Monoxide (CO) Test: Carbon monoxide will be measured at each in-person visit to confirm smoking status.

Other Smoking Measures (secondary)

As per recommendations (Hughes et al., 2003), we will also assess: prolonged abstinence to Weeks 12, 24, and 52 (relapse is 7 consecutive days of self-reported smoking, after a 2-week grace period), continuous abstinence at Weeks 12, 24, and 52 (no smoking between the quit day and follow-up), time to 7-day relapse (no grace period), smoking rate, and lapse (smoking episodes < 7 days) and recovery (return to 24-hour abstinence) events.

Quality of Life (QOL)

The Short-Form Health Survey (SF-12) will assess QOL (Ware et al., 1996). This scale yields physical and mental subscales, has been used to assess cancer patient QOL (McCorkle et al., 2009), has demonstrated validity and reliability (Gandek et al., 1998), and has been used in smoking cessation trials with cancer patients ([name] et al., 2010a). The SF-12 will be administered at all visits following the Intake Session.

2. Statistical Analysis

Power

Power is provided for the primary aims since the exploratory aim is hypothesis generating. All comparisons are 2-sided.

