Aim 3: The analyses will assess changes in affect and cognitive impairment as mediators of treatment arm effects at Week 24 and 52. These measures are continuous difference scores. Our sample of 374 is well above the minimum sample of 200 recommended for models of this size (Haduk, 1987; Boosma & Gabrielli, 1985). The mediation hypothesis will examine the proportion of treatment effect explained (Lin et al., 1997; Vittinghoff et al., 2009), and test with a z-score generated using the delta method. Our sample of 374 gives us 80% power to observe small effects in a 1-sample test ($\delta=0.20$) when testing at $\alpha=0.05$. There are two proposed mediating pathways between treatment and outcome, so our type-1 error will be corrected to 0.025. Our sample of 374 gives us 80% power to detect small to medium effects ($\delta=0.22$) for changes in the proposed mediators.

[figure not shown]
Data Analysis

[name] will oversee analyses. Preliminary analyses will assess sample characteristics by treatment with chi-square or logistic regression (e.g., gender, dependence, depression, disease site). These variables will also be examined for their relationship to completion of outcome assessments. Variables related to treatment arm and completion of follow-ups will be included as covariates in analyses of study aims. Compliance measures will be evaluated across treatment arms, and controlled for in primary analyses. Although we will use an intent-to-treat analysis as the primary method for evaluating study aims, we will conduct a completers only analysis of study aims and examine study aims with participants lost to follow-up due to death excluded as done previously ([name] et al., 2003).

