Aim 3: Assess changes in affect and cognitive impairment and cue-elicited urges as mediators of extended varenicline therapy's effect on quit rates. The effects of treatment arm on mediators will be assessed using linear regression. Structural equation modeling will be used to obtain a more comprehensive understanding of these mechanisms. It is hypothesized that treatment arm will yield significant differences in proposed mediators and that differences in mediators will predict week 24 and 52 outcomes. We will focus on changes in mediators from baseline to week 14, when the standard therapy participants transition to placebo and the extended therapy group stay on active treatment. After first demonstrating that treatment arm affects quit rates (Aim 1), these effects will be partitioned into mediated and unmediated effects, via path and structural equation models. For example, paths *d* and *b* represent the mediated effects of treatment arm on quit rates through changes in negative affect, and path *a* represents residual effect of treatment arm on quit rates not mediated by negative affect. Path *f* represents the hypothesis that the impact of treatment arm on quit rates will depend on negative affect. Specific hypotheses will be tested by using chi-square difference tests that contrast the overall fit of this full model with more parsimonious nested models in which specific predictive effects are fixed to zero (e.g., the unmediated path *a*). Model goodness-of-fit indices will be contrasted to guide interpretation of results and determine the practical significance of statistically significant differences. Modification indices will be examined to guide model interpretation and modification. Models will be tested through Mplus, which easily accommodates the combination of binary and continuous variables. This approach allows us, in principle, to test whether treatment effects on quitting are due to specific mechanisms (e.g., reduction in negative affect). Tests for mediation by positive affect, withdrawal, cognitive impairment, and cue-elicited urges will be conducted in this fashion.

Path Model of Treatment Arm, Negative Affect, & Quit Rate

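### Aim 3 tests the arm effect on raw mediator change scores and does not name the collected Week 0 score as a covariate, so precision that costs nothing may be lost

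*Combined protocol and SAP*

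**What the plan says.** Under 2. Statistical Analysis, Power, Aim 3, the mediators are defined: "These measures are continuous difference scores". Under Data Analysis, Aim 3, the model is "The effects of treatment arm on mediators will be assessed using linear regression", and the time frame is set: "We will focus on changes in mediators from baseline to week 14". No covariate is listed for this regression.

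The power text for the same step reads "Our sample of 374 gives us 80% power to detect small to medium effects", with a standardised effect of 0.22. The error rate comes from "There are two proposed mediating pathways between treatment and outcome, so our type-1 error will be corrected to 0.025", and the Power section opens by saying "All comparisons are 2-sided".

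Table 2 and the Mediating Variables section schedule the PANAS, FACT-Cog, withdrawal form and QSU-B at both Week 0 and Week 14. The baseline value is therefore in hand for each of these scales.

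**The concern.** Regressing a difference on arm forces the coefficient of the baseline score to equal 1. The best-fitting coefficient is usually smaller, because scores taken 14 weeks apart, with a quit attempt in between, are unlikely to be perfectly correlated. The excess noise falls on the arm-to-mediator step, which is the first link that any mediation claim needs.

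The second link is affected too. A difference score is correlated with its own baseline. The Background section describes distress and withdrawal-related cognitive impairment as predictors of relapse. If baseline level also predicts quitting, the path from change to quitting is confounded by baseline, and randomising the arms does not protect that path.

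**Working it through.** **Inputs from the documents.** N = 374; alpha 0.025, two-sided; effect 0.22 with 80% power (Power, Aim 3). About 70% are expected to complete follow-up (Accrual).

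**Assumptions.** Allocation 1:1, so n = 187 per arm. The plan states no ratio; its 187 is a per-site figure ("total sample at PENN = 187 over 4 years"). The Week 0 to Week 14 correlation rho is taken from 0.3 to 0.8. The SD ratio k = SD(Week 14)/SD(Week 0) is 1 in the base case. The documents give neither rho nor k.

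**Step 1: the plan's own figure.** Two-arm power is Φ(δ√(n/2) − z), with z = 2.241 for two-sided 0.025.

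- δ√(n/2) = 0.22 × √93.5 = 2.127, and Φ(2.127 − 2.241) = 45.5%. The stated 80% is not reproduced.
- 80% power needs δ = (2.241 + 0.842) × √(2/187) = 0.319, or 393 patients per arm at 0.22.
- Read as a one-sample test, 374 patients give 97.8% and 187 give about 78%. The latter is the nearest match. The companion statement for the mediation test does refer to a one-sample test ("Our sample of 374 gives us 80% power to observe small effects in a 1-sample test").

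Both starting points are carried forward: an assumed 80% and the recomputed 45.5%.

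**Step 2: variances.** With Week 0 variance s²:

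- change score: s²(1 + k² − 2ρk)
- baseline-adjusted: s²k²(1 − ρ²)
- first minus second: s²(1 − ρk)², which is never negative

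So adjustment is never less precise in large samples, apart from one degree of freedom. It gains nothing when k = 1/ρ. The ratio of adjusted to change-score variance is R = k²(1 − ρ²)/(1 + k² − 2ρk), which is (1 + ρ)/2 when k = 1.

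**Step 3: power with equal SDs (k = 1).** From 80%: Φ(3.083/√R − 2.241). From δ = 0.22: Φ(2.127/√R − 2.241).

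| rho | R | from 80% | gain, points | from 45.5% | gain, points |
|---|---|---|---|---|---|
| 0.3 | 0.65 | 94.3% | 14 | 65.4% | 20 |
| 0.5 | 0.75 | 90.6% | 11 | 58.5% | 13 |
| 0.7 | 0.85 | 86.5% | 6 | 52.6% | 7 |
| 0.8 | 0.90 | 84.3% | 4 | 50.0% | 5 |

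**Step 4: unequal SDs, from 80%.**

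- k = 1.25: 84.6% at rho 0.5 and 80.8% at 0.7. At rho 0.8, R = 0.36 × 1.5625/(1 + 1.5625 − 2) = 0.5625/0.5625 = 1, so there is no gain.
- k = 1.5, rho 0.5: 81.5%.
- k = 0.8, rho 0.5: 96.7%.

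**Step 5: incomplete data.** With 70% completers, 0.70 × 187 ≈ 131 per arm. At δ = 0.22 and rho 0.5 (k = 1), power goes from 32.2% to 42.6%, about 10 points.

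**Step 6: the quit path.** With equal SDs the correlation of change with its own baseline is −√((1 − ρ)/2): −0.50 at rho 0.5 and −0.39 at 0.7. How far this biases the mediated effect cannot be computed from the documents.

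**The case against.** The plan is silent about the baseline score; it does not rule it out. Data Analysis has a general rule that adds variables found to be associated with arm and with completion of follow-up. The HADS is described as serving both as mediator and as covariate. The path diagram is not available in the text, so whether baseline affect appears in it cannot be checked. A reader might infer that the plan rejects baseline adjustment; the documents do not support that.

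The general rule is still a weak answer. Under randomisation a baseline score is associated with arm only by chance, and the rule selects on imbalance and missingness, not on prognostic strength. The HADS remark names no model, and the HADS is not the baseline of the other scales.

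A reader might also take a loss of about 10 points as a property of this trial. It is not. That figure needs a correlation of 0.5, equal SDs, an 80% start and complete data, none of which the documents establish. Step 4 shows that the gain can vanish.

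Nor is the arm comparison on change scores biased: randomisation keeps it valid, and on that step the issue is precision alone. Finally, Aim 3 is not the primary analysis, the effect is partitioned only after Aim 1 shows one, and the power of the full mediation test also depends on the mediator-to-quit path. All of this limits the consequence without removing the omission.

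**Conclusion.** The point holds as an unspecified covariate on a non-primary aim, with a free improvement available. Baseline adjustment is asymptotically at least as precise as the raw difference, whatever the correlation and SDs. Its size in this trial is unknown. With equal SDs, 1:1 allocation, complete data and an 80% start at two-sided alpha 0.025, it is worth about 14 to 4 points of power over correlations of 0.3 to 0.8. From the plan's effect of 0.22 read as a two-arm contrast it is worth about 20 to 5 points. It approaches zero as the Week 14 SD rises towards 1/rho times the Week 0 SD. The gap between the stated 80% and the recomputed 45.5% is larger than any of these gains under equal SDs, and it makes the unused precision harder to justify.

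**What to change.** In Data Analysis, Aim 3, for the PANAS, FACT-Cog, withdrawal form and QSU-B, regress the Week 14 score on arm with the Week 0 score of the same scale as a pre-specified covariate. In the path model, use the Week 14 score as mediator and let the Week 0 score predict both the mediator and quitting. In Power, Aim 3, replace the difference-score definition to match.

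Cue-elicited urges need a separate sentence. Table 2 schedules the choice task at Weeks 0, 1, 4, 12, 24 and 52, so there is no Week 14 value. Apply the same baseline adjustment at Week 24, the first scheduled task after Week 12, when the arms diverge. Relate that mediator only to Week 52 quitting, because at Week 24 it is concurrent with the outcome.

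The cost is wording in two places. No new data or visits are needed, and the randomised comparison stays valid. Fixing the model in advance also removes a later choice between the change-score and adjusted analyses.
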